12.5 Interim Analysis

The interim analysis will be conducted following completion of the study by 77 patient-caregiver dyads (half-way point) for safety and efficacy monitoring. At this time, adverse events, drop-out rates, and missing data will be reviewed in entirety. Stopping rules will be applied when appropriate. The interim analysis will take place with the involvement of the Research Coordinator, Study Biostatistician, Safety Officer, and PI. The decision to continue the study must be unanimous among these 4 parties.

13.0 Data Management

The Regenstrief Institute has the capacity to safely collect and secure research and clinical data, and a long track record of doing so. To minimize the risk of breach of confidentiality, all study materials will be regarded as strictly confidential. Paper study documents will be stored in a locked filing cabinet in a secure office at the Regenstrief Institute, IU Center for Aging Research. Data will be extracted into a pre-designed

REDCap database stored behind the IU firewall. The study team will not collect any additional data without the consent of the participant and the Indiana University IRB. Computerized data entry and data storage systems are password protected and will be accessible only to study personnel.

Additionally, each participant will be given a unique identifier. Their data will be stored only using the unique identifier. A key that matches the unique identifier with identifiable data (name, dob, mrn) will be stored securely behind the IU firewall. All research study personnel have completed training in Human Subjects Research and HIPAA standards.

Screening data obtained from EMR and phone calls will be collected on paper, stored in a secure office and locked file cabinet in the Regenstrief Institute, Inc. In the instance a potential participant refuses enrollment, the paper document with screening data will be destroyed.

Participant data entered by the participant into the mobile application (BCN intervention) will be stored on an Amazon Web Services, HIPAA secure server and transferred into a secure REDCap database located behind the Indiana University Firewall.

Participants will be asked to give consent to have their interviews recorded. Audio recordings will be transcribed into an electronic word document form. Both the audio recordings and word document will be stored on a secure Regenstrief Institute. Once transcribed audio recordings will be destroyed.

13.1 Protection Against Study Risks

We will only approach potentially eligible patients and caregivers. Both members of the dyad or a legally authorized representative (LAR) need to consent to participate in the study. The PI will be available to clarify any questions and offer any needed consultation during the consent process or data collection process. Participants will be informed that representatives of the IRB or other regulatory bodies may inspect their study records to verify the information collected and that all information will be handled in strictest confidence. All analyses from the study will be performed and reported in aggregate and will exclude any personally identifying information.

To minimize potential anxiety on the part of patients or their family members, we will emphasize that participation is completely voluntary, that all information will be regarded as confidential, and that the subjects do not have to answer any questions they are uncomfortable answering. To minimize the risks that our intervention would have any negative impact on the dyad, we will monitor caregiver reporting of BPSD and caregiver stress, and burden of answering questions.

Additionally, if the patient's SECBCI treating physician objects to any patient's participation in the study because they believe it may have a negative impact on care may refuse to allow us to contact the subject to participate.

13.2 Rigor and Reproducibility: will be maintained through: 1) testing of the REDCap

database by study team prior to moving to production mode, 2) monthly audits of data entry into the REDCap database while the study is active and strict adherence to the proposed study protocol confirmed by audits of study team assessments.

14.0 Privacy/Confidentiality Issues

A recruitment waiver has been requested, for several reasons: (1) the eligibility criteria for participation is specific enough that any other recruitment method would result in inadequate recruitment, (2) bringing an individual with aMCI/AD to a medical or research appointment can be stressful for both the patient and the caregiver and calling the patient-caregiver dyad prior to their SECBCI appointment to gauge their interest in research has the potential to reduce stress, by reducing unexpected events and planning, 3) by allowing a recruitment waiver we will be able to receive the patient's most recent mini-mental status exam (MMSE) score, a measure of dementia severity that will be used in part to judge whether the patient has capacity to consent to research, and (4) this will allow the research team to seek the patient's SECBCI physician input to on whether or not he or she believes the patient to have capacity to consent to research.

Without access to MMSE scores and physician input, there would need to be more extensive testing burdensome to the patient and caregiver to determine if the patient has capacity to consent for research. Screening data will be destroyed immediately after learning that the patient-caregiver dyad declines interest in the study or declines study enrollment and for those who consent to the study screening data will be destroyed immediately following enrollment.

With the exception of screening information that will be destroyed if the patient-caregiver declines interest in the study, no data included in the study will be recorded without the consent of the patient-caregiver dyad. During the baseline research visit (point of consent), throughout the 6-month study, including the 3-month visit and the final visit, the caregiver will be asked questions about dementia, stress, coping and about difficult behaviors and psychiatric symptoms of dementia. It is possible that some of these questions could cause anxiety or discomfort. To minimize risk the caregiver is made aware that these types of questions will be asked ahead of time. The caregiver is also given the option to not answer the questions or to stop at any time.

As a part of the informed consent the caregiver-dyad will be asked to give consent for investigators to look at the patient's SECBCI medical records. There is the possibility that there could be a loss of confidentiality. We will minimize this risk by following the Regenstrief Institute, Indiana University Center for Aging Research data management and quality assurance practices as a method to mitigate risk for loss of confidentiality.

Additionally, each participant will be given a unique identifier. Their data will be stored only using the unique identifier. A key that matches the unique identifier with identifiable data (name, dob, mrn) will be stored securely behind the IU firewall. All research study personnel have completed training in Human Subjects Research and HIPAA standards.

15.0 Follow-up and Record Retention

The duration of the study will last for 5 years (6 months per each subject) or when enrollment and study activities of 154 patient-caregiver dyads is complete, whichever happens first. Paper data and electronic data will be kept for 5 years, at which point paper-based data will be securely destroyed in line with standard Regenstrief Institute procedures.

16.0 Other

16.1 Essential Equipment: We will use the Android Pixel phone by Google as a loaner phone for study subjects (caregivers) who do not have their own smartphone. The phone will be pre-loaded with the EMA version of the NPI-Q delivered by mobile app.

16.2 Potential Problems and Alternative Strategies:

16.2.1 Worsening caregiver burden: One concern of this proposal, is whether EMA monitoring of BPSD creates too much of a burden on the already burdened caregiver. Participants in our 28-day R01 study and in our pilot have not found the EMA pinging of the smartphone to be burdensome. The R01 study population demographics overlap significantly with our anticipated patient-caregiver population. As a safeguard, we will use usability and burden questions from the semi-structured interview from the initial 10 aMCI/AD caregiver-dyads to determine if the burden of answering EMA questions for the caregivers is too great. If that does turn out to be the case we will consider lengthening the surveillance interval or shortening the assessment battery.

16.2.2 Drop off in participation during the monthly response interval: It is possible that participation in the EMA BPSD surveillance might drop off during the two-month block, where BPSD surveillance takes place monthly instead of weekly. To address the potential, drop off in participation during the monthly surveillance block we will observe attrition rates for our first 10 dyads. If attrition rates exceed that of 17% we will make an adjustment to surveillance frequencies dropping the monthly surveillance block and instead continuing with weekly surveillance.

16.3 Summary and Future Directions: The following study looks to improve the care of aMCI/AD patient-caregiver dyads through the study of a BPSD surveillance intervention. Our choice of a weekly/monthly frequency, was a conservative approach in this early work to manage caregiver and provider burden but should evidence indicate high feasibility and value of weekly intervals, a future project could test higher frequencies to identify a frequency of diminishing return. Findings from this study will be used to develop a BPSD surveillance EMA intervention for a future R01 proposal that will improve the access to care and health of AD patient-caregiver dyads. This work will help my maturation into an independently funded investigator.

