6.2 Preliminary Work: Neuropsychiatric Inventory Questionnaire (NPI-Q) –

Ecological Momentary Assessment (EMA) Caregiver Pilot: We successfully pilot tested the NPIQ-EMA app in four AD patient-caregiver dyads without any attrition. The time horizon for the pilot differs from the proposal in that the caregiver was asked to fill out the smartphone survey (NPIQ-EMA) daily for a 2-week time period. Patient ages ranged from 63 to 95, and caregiver ages ranged from 63 – 82. Three of four caregivers identified as African American. All four caregivers found answering the NPIQ-EMA questions to “Not be burdensome.” Several caregivers reported that the NPIQ-EMA improved their awareness of the patient’s BPSD. Three of four answered that they would prefer weekly monitoring rather than daily and the last caregiver expressed a preference for daily monitoring. All caregivers agreed that the system was easy to use.

6.3 Recruitment, Screening, Informed Consent, and Enrollment: The Sandra Eskenazi Center for Brain Care Innovation provides longitudinal care to ~ 600 patients; 38.7% are Black; and 70.4% are female. In addition, each of five clinicians completes an initial assessment on 1-3 new patients per week. We anticipate a recruitment number of 154 dyads over 27 months and believe this to be achievable. Half of the dyads would be randomized to the intervention or treatment as usual group. Our group has a recruitment rate of approximately 50% of eligible subjects in this environment⁴³.

6.4 Randomization Scheme: Participating dyads will be randomized to the two groups (intervention vs control) using a randomization list that contains group assignment in blocks, thus ensuring that the groups have comparable sample sizes throughout the study. We will use a stratified block random assignment following the Kernan strata determination formula (Kernan et al. 1999) listed as, $\# \text{ of strata} < n / B \times 4$, where B is block size and “... n is the sample size at the first planned interim analysis and 4 is a safety factor that accounts for unequal distribution of patients among strata.” Using $n=154$ and $B=4$, then, the $\# \text{ of strata} < 9$. In this study, we will use 8 strata = 2 Diagnosis (aMCI, AD) x 2 Gender (M, F) x Age (< 65, \geq 65). Sealed envelopes with randomization assignments will be prepared by a research team member not involved

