In the original power justification, we used a Cohen's d effect size of 0.65, which is between a medium (0.50) and a large (0.80) effect size. This was done primarily because of budgetary constraints associated with the K23 funding mechanism, which limited our ability to detect effect sizes smaller than 0.65 by enrolling beyond the proposed 96 dyads. However, with additional institutional funding support for 40% RA effort over 30 months we are now able to accommodate an enrollment sample size of 154 dyads (77 in each group), resulting in a projected 64 analyzable participants in each arm (control and intervention) after accounting for an attrition rate of 17% seen in the previously noted in the protocol trial (Callahan et al., 2006; Calculation = $(64 \times 2)/0.83 = 154$). The analyzable sample of 64 per arm for two-tailed tests of two independent populations will provide 80% power (using alpha = 0.05) to detect a medium effect size of 0.50, which is a common effect size chosen in both R01 and K-series proposals. The power for paired within-group tests between weekly vs monthly conditions for the 64 analyzable intervention participants will be slightly greater than 80% power. Selecting a medium effect size of 0.50 matches the effect size seen in the aforementioned non-pharmacologic protocol trial, where effect sizes for total NPI score and NPI caregiver distress score improvements at 12 months were 0.502 and 0.568, respectively (Callahan et al., 2006). We expect that this would require approaching 12 dyads per month and consenting and enrolling 6 dyads per month (1-2 dyads per week) over a span of 30 months.

The SECBCI practice employs 6 physicians each with a half day clinic where they see between 4 and 9 patients on any given half day. Meaning that a range of 24 – 54 total patients are seen per week, with over one third of patients carrying a diagnosis of AD, leading to projections of between 8 – 18 eligible patients per week. Our prior work has consistently shown a recruitment rate of 50% for eligible patients, meaning that it would be reasonable to expect a maximal consent and enrollment rate of 4 – 9 subjects per week, a number much greater than the required study recruitment number of 1 – 2 subjects per week.

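### The section 16.2.2 rule for dropping the monthly condition is set at the planned 17% attrition and judged on 10 dyads, so it can fire by chance with attrition on plan

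*Combined protocol and SAP*

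**What the plan says.** Section 16.2.2 worries that participation "might drop off during the two-month block, where BPSD surveillance takes place monthly instead of weekly". Its safeguard is that "we will observe attrition rates for our first 10 dyads", followed by the rule "If attrition rates exceed that of 17% we will make an adjustment to surveillance frequencies dropping the monthly surveillance block", after which surveillance continues weekly. It gives no look time, no arm, and no definition of which losses count.

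Section 12.4 sizes the trial "after accounting for an attrition rate of 17" per cent, giving 64 analysable dyads per arm from 77 enrolled. It relies on those 64 for the frequency comparison: "The power for paired within-group tests between weekly vs monthly conditions for the 64 analyzable intervention participants will be slightly greater than 80% power".

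Three other places bear on the rule:
- Table 1 (section 5.0) says the frequencies will be looked at again, and may be changed, after feedback from the first 10 intervention-arm participants. That is discretionary wording tied to one arm.
- Sections 5.0 and 6.4 have every intervention dyad switch frequency each month for six 1-month periods. No two-month block exists in that design.
- Section 16.2.1 uses the initial 10 dyads for a different purpose. If burden is too great, "we will consider lengthening the surveillance interval or shortening the assessment battery".

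**The concern.** The trigger equals the expected value. A rule meant to detect unusual loss should rarely fire when loss is as expected. Here 1 loss in 10 (10%) does not fire it and 2 in 10 (20%) does, so ordinary sampling variation can remove a randomised condition.

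The rule may also be unable to answer its own question. Each intervention dyad alternates between weekly and monthly prompts, so overall attrition cannot show that the monthly condition is the cause. The section starts from a drop in participation but acts on attrition. A caregiver may stop answering prompts without leaving the study, or leave for reasons unrelated to frequency.

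At stake is the within-group comparison of weekly with monthly surveillance in H2 (secondary) and H3 (exploratory), and the objective in sections 1.0 and 5.0 of finding the optimal frequency. Dyads followed after the rule fires contribute nothing to either. Section 12 describes no analysis for that case.

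**Working it through.** **Plan's own figure.** (64 × 2)/0.83 = 154.2, stated as 154; 77 × 0.83 = 63.9, stated as 64. Both reproduce, so 17% is the planned loss.

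**Inputs.** Ten dyads and a threshold above 17% (16.2.2); 17% attrition (12.4); six alternating 1-month periods (5.0, 6.4); 1:1 allocation (5.0). Assumptions: the 17% is 6-month attrition, and the hazard is constant. The overall 6-month figure needs only the first assumption.

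**Chance of firing.** With loss probability p per dyad, P = 1 − (1−p)^10 − 10p(1−p)^9.

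For overall attrition at 6 months, p = 0.17: 1 − 0.155 − 0.318 = 0.527.

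For other look times, p = 1 − 0.83^(m/6) after m months. For losses in monthly months only, let q = 1 − 0.83^(1/6) = 0.0306 and s = 1 − q. Over 6 months, p = q(1 + s² + s⁴) for a monthly start and q(s + s³ + s⁵) for a weekly start. Over 3 months, p = q(1 + s²) and qs respectively.

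| Losses counted | Look | p | P(2 or more of 10) |
|---|---|---|---|
| Monthly months, all start monthly | 6 months | 0.0863 | 21.1% |
| Monthly months, all start weekly | 6 months | 0.0837 | 20.2% |
| Monthly months, all start monthly | 3 months | 0.0593 | 11.5% |
| Monthly months, all start weekly | 3 months | 0.0296 | 3.4% |
| Overall | 6 months | 0.170 | 52.7% |
| Overall | 3 months | 0.0890 | 22.1% |
| Overall | 2 months | 0.0602 | 11.8% |

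Five dyads on each starting frequency give 7.0% for monthly-month losses at 3 months. Section 12.4 gives no period for the 17%. If it accrued over 12 months, p at a 6-month look is 1 − 0.83^(6/12) = 0.0890, and overall attrition fires 22.1% of the time.

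**Dyads left for weekly versus monthly.** The look is taken on the first 10 intervention dyads, L months after the tenth enrols. The documents give two enrolment statements: "We anticipate a recruitment number of 154 dyads over 27 months" (6.3) and "consenting and enrolling 6 dyads per month (1-2 dyads per week) over a span of 30 months" (12.4). They imply 154/27 = 5.70, 154/30 = 5.13, or 6 dyads per month. Half go to the intervention arm, so r = 2.85, 2.57 or 3.00 per month. Intervention dyads enrolled by the look number 10 + rL; those enrolled at least 2 months earlier number 10 + r(L − 2).

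- If dyads in progress finish the alternating schedule, retention is 0.83.
- If both conditions must already have been completed, only 2 months are needed and retention is 0.83^(1/3) = 0.94.

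| Look | Rate per month | Finish schedule | Both conditions completed |
|---|---|---|---|
| 6 months | 5.13 | 25.4 × 0.83 = 21.1 | 20.3 × 0.94 = 19.1 |
| 6 months | 5.70 | 27.1 × 0.83 = 22.5 | 21.4 × 0.94 = 20.1 |
| 6 months | 6.00 | 28.0 × 0.83 = 23.2 | 22.0 × 0.94 = 20.7 |
| 3 months | 5.13 | 17.7 × 0.83 = 14.7 | 12.6 × 0.94 = 11.8 |
| 3 months | 5.70 | 18.6 × 0.83 = 15.4 | 12.9 × 0.94 = 12.1 |
| 3 months | 6.00 | 19.0 × 0.83 = 15.8 | 13.0 × 0.94 = 12.2 |

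**The case against.** The best defence is that 16.2.2 sits under potential problems and alternative strategies, that its heading points to losses in monthly months, and that Table 1 already treats any change as discretionary. On that reading the chance of firing is 20% to 21% at most, and 3% to 12% at an early look. There is also oversight: the Safety Officer sees drop-out rates quarterly (Table 5) and may recommend modifications (10.6), and the IRB or the funder makes the final decision on a recommendation to discontinue a study component (10.7). Much of this stands as a limit on size. It does not cure the wording, because 16.2.2 commits the team to act and does not refer to that route.

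Four stronger readings are tempting, and the documents do not support them:
- A reader might infer that the rule fires more often than not. The 53% needs overall attrition and a full 6-month look, and the text fixes neither.
- A reader might take the first 10 dyads to span both arms. With about 5 intervention dyads, 1 loss would exceed 17%, at 1 − 0.83^5 = 61% over 6 months. Table 1 names the intervention arm, and only that arm has a monthly condition, so this is unlikely.
- A reader might want a power figure for the reduced sample. Section 12.4 states no paired standardised difference for its within-group claim, and H2 is a binary monthly endpoint in a mixed nonlinear model, so any such figure would rest on an invented input.
- A reader might conclude that the trial fails. The primary feasibility outcome remains, and so does the comparison with control.

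**Conclusion.** The concern holds in a limited form. Section 16.2.2 states a mandatory rule whose trigger equals planned attrition, judged on 10 dyads, with look time and counting rule unstated. With attrition on plan, it fires 3% to 21% of the time on the reading the heading suggests and 12% to 53% on the bare wording, for the look times shown. These figures treat 17% as 6-month attrition; all but the 53% also assume a constant hazard.

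If the rule fires, about 21 to 23 analysable dyads remain for weekly versus monthly at a 6-month look, or 15 to 16 at 3 months, when dyads in progress finish the schedule. If both conditions must already have been completed, the counts are about 19 to 21 and about 12. The intervention-versus-control comparison continues, but with an intervention that changes part-way.

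This is more than missing detail, because the commitment in 16.2.2 contradicts the discretion in Table 1. The conflict with 16.2.1 is only potential: one safeguard may lengthen the interval while the other removes the longer one, and no order of precedence is given.

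**What to change.** 1. Make the look at the first 10 dyads a prompt for review, in line with Table 1, and not an automatic removal of the monthly condition.
2. Base it on drop-out and NPI-Q completion in monthly versus weekly months within the intervention arm. State the look time and define a loss.
3. If frequencies are changed, restrict the within-group H2 and H3 analyses to dyads followed under the alternating schedule, and report the reduced precision.
4. Reconcile 16.2.2 with Table 1 (arm and discretion), with the 1-month periods in 5.0 and 6.4, and with 16.2.1.

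The cost is protocol and analysis wording only. The downside is that a real retention problem in the monthly condition may be acted on later. A stricter automatic cut-off is not proposed, because 10 dyads cannot support one: on overall attrition at 6 months, requiring 3 or more losses still fires 23% of the time at a true 17%, and only 62% at a true 30%.
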